### 8.1.1 Washout Restrictions during Part 1 of the Study Only

The washout period for LAMA or LABA is as follows:

- LAMA medications (including mono products and combination products containing LAMAs [eg, LAMA/LABA]) will not be permitted within 21 days of the screening visit (visit 1) and throughout the study (except for the study medication provided at each treatment period). Any patients taking LAMA medications will need to discontinue these medications, and at the Investigator's discretion, the LAMA may be replaced with ipratropium bromide (SAMA), adhering to the washout restrictions below.
- LABA mono products will need to be discontinued 7 days before the screening visit (visit 1) and throughout the study. Any patients taking LABAs will need to discontinue these medications, and at the discretion of the Investigator, the LABA may be replaced with ipratropium bromide (SAMA), adhering to the washout restrictions below.
- ICS/LABA combination products will need to be discontinued 30 days before the screening visit (visit 1) and throughout the study. Any patients taking

ICS/LABAs will need to discontinue these medications, and at the discretion of the Investigator, the ICS/LABA may be replaced with ipratropium bromide (SAMA), adhering to the washout restrictions below

Patients should refrain from taking the following medications from the specified time points below prior to spirometry assessments at each clinic visit (both days of each inpatient visit) during Part 1 of the study:

- SABAs 6 hours
- SAMAs: 8 hours
- short-acting forms of theophylline: 12 hours
- twice-a-day controlled-release forms of theophylline: 24 hours
- once-a-day controlled-release forms of theophylline: 36 hours
- caffeine-containing medications (eg, MIDOL®, EXCEDRIN®) 6 hours

If a patient requires the use of a SABA for rescue during the serial spirometry, the administration of the rescue medication should be recorded as a protocol deviation and the patient should continue with the pulmonary function testing as scheduled for that day.

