## 9.2 STUDY PROCEDURES

### 9.2.1 Efficacy Procedures

#### 9.2.1.1 Spirometry (Part 1 Only)

##### FEV1

The spirometry endpoint data will be captured using standardized equipment supplied by a central spirometry vendor. This equipment will meet or exceed the ATS/ERS recommendations for forced spirometry testing equipment, and spirometry measurements will be performed according to ATS guidance document recommendations to ensure both technical acceptability and repeatability of test data (Miller 2005). The test data will be overread by the central spirometry provider and any discrepancies in relation to the best test effort will be communicated back to the investigational center.

Spirometry testing will be performed by experienced research staff who have passed a proficiency process to ensure understanding of the equipment used and forced spirometry technique. To collect data in a consistent manner, the same staff member will conduct all spirometry assessments for the same patient whenever possible. The same spirometer should be used on a patient throughout the study. Onsite spirometry assessments (baseline/study qualifying/reversibility) must occur after washout of the protocol prohibited and restricted medications.

Patients should be at rest for approximately 15 minutes prior to testing and should be comfortable. Tight clothes should be loosened to allow the thorax to move freely; the patient should be seated in an upright posture and with a nose clip in place. The patient should not smoke or have been in a smoky atmosphere for at least 1 hour prior to each FEV1 assessment, should have avoided highly caffeinated drinks for at least 6 hours, and should have adhered to the restricted medication criteria for the appropriate time as outlined in section 8. If these criteria have not been met, the patient should have the visit rescheduled.

All visits to the investigational center for Part 1 must be scheduled in the mornings between 0600 and 1000 and spirometry testing should begin at  $\pm 1$  hour of the start of visit 1 study qualifying spirometry testing time. Predose FEV1 measurements will be recorded at 0 hours (-30 and -15 minutes before administration of study medication) at the investigational center at visits 1 through 4; serial FEV1 measurements will be recorded postdose at 5 and 30 minutes, and at 1, 2, 4, 6, 8, 10, 12, 23, and 24 hours.

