9.11 Methods for Handling Dropouts and Missing Data

Missing efficacy data will be handled in the following ways:

For missing serial spirometry measurements:

Missing data methods will be used provided that at least 9 of the 11 post-dose serial spirometry measurements are available. Linear interpolation between the 2 adjacent FEV₁ measurements will be used to estimate missing spirometry measurements occurring between 2 available measurements. The exception to this would be the unlikely event of missing measurements that occur near the peak of the FEV₁ -time curve, expected to occur between 30 min to 2 hours post dose. In these cases the average percentage change from the preceding value for patients receiving the same treatment will be used. This makes use of the response of other patients to the same treatment. For analysis, the percentage will be expressed in terms of an FEV₁ value.

For missing measurements at the end of the time profile (i.e., no available FEV₁ value after a point in time):

- For values at the end of the profile that were missing because rescue medication was taken, the minimum observed FEV₁ value on that test day, including the predose

Sponsor: Lupin Inc.
Protocol no: TB-DPI-301

value, will be used as the estimate. This is similar to assuming that there would be no increase from baseline after the point that rescue medication was required.

- For values at the end of the profile that were missing for reasons unrelated to the patient's response to treatment, the average percentage change from the preceding values for patients receiving the same treatment will be used. This makes use of the response of other patients to the same treatment. For analysis, the percentage will be expressed in terms of an FEV₁ value.
- For values at the end of the profile that were missing for unknown reasons, the observed minimum FEV₁ value on the day of testing, including the pre-dose value, will be used as an estimate. This conservatively assumes that there would be no increase from baseline after the point that the data were missing.

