Two additional sensitivity analyses will be performed, where the missing data rules for the tail end of the profile will be based on the following: (a) the AUC calculation will be based on the time interval up to the last non-missing time point, and will then be standardized by dividing by the length of time for which FEV₁ measurements were included (ie. the AUC will be a weighted average), and (b) the baseline value will be substituted for the missing values.

If a patient contributes data to at least 2 of the crossover legs, data from that patient will be included in the analysis as the patient will have provided data for one of the treatment comparisons. If a patient completes only 1 leg of the crossover, data from the patient will be listed but will not be included in summary statistics or the analysis. There is no reasonable basis for imputing data for a completely missing leg of the crossover.

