10.2 Per Protocol

The Per Protocol (PP) analysis population will be the primary analysis population used for the determination of BE between the Test and Reference products. The PP analysis population will exclude patients from the ITT population who have major protocol deviations in Part 1 of the study on either the Test treatment day or the Reference treatment day. Patients may have a major protocol deviation on the Placebo treatment day and still be

Sponsor: Lupin Inc.
Protocol no: TB-DPI-301

included in the Per Protocol population that will be used to assess BE although data from the Placebo day will be excluded from the analysis.

All patients with a major protocol deviation will be identified before the study blind is broken, and the removal of a patient from a treatment period will be documented within the clinical trial management system's protocol deviation file. In addition, individual FEV1 values from a patient may be removed from their 24-hour serial curve, including the 2 predose measurements, if they were the result of poor quality spirometry efforts. In those cases, the value will be set to missing and missing value rules applied as described in [Section 9.11](#).

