13.2 Protocol Deviations

The study team and the sponsor will conduct on-going reviews of the deviation data throughout the study. The PP population must be identified prior to database lock.

Sponsor: Lupin Inc.
Protocol no: TB-DPI-301

Protocol deviation data will be categorized into one of the following categories:

- 01-Inclusion/Exclusion/Randomization Criteria
- 02-Continuation Criteria
- 03-Spirometry Evaluation
- 04-Study Procedures
- 05-Study Drug
- 06-Out of Window Visits
- 07-Informed Consent
- 08-Prohibited / Restricted Medications
- 09-Other
- 10-Diary
- 11-ICH/GCP

Each deviation will be further classified as major/minor as defined in the protocol deviation guidelines. A summary of the number of patients with major deviations will be presented by category and treatment for Part 1 and Part 2 of the study separately. All protocol deviation data will be listed.

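### The SAP's rescue rule acts only on missing values, but testing continues after rescue, so bronchodilated FEV1 readings enter the primary AUC or else the 9-of-11 condition blocks the rule

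*SAP*

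**What the plan says.** SAP 9.11 has a minimum-value rule for rescue: "For values at the end of the profile that were missing because rescue medication was taken", the lowest FEV1 of that test day, predose included, is used. The SAP explains that this resembles assuming no increase from baseline once rescue is needed. The rule sits under a lead-in that defines the tail as "no available FEV₁ value after a point in time".

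Protocol 8.1.1 says rescue during serial spirometry is recorded as a deviation and "the patient should continue with the pulmonary function testing as scheduled for that day".

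SAP 9.11 also sets a minimum: "Missing data methods will be used provided that at least 9 of the 11 post-dose serial spirometry measurements are available". Protocol 11.5.3 has the same tail rules without this condition. Under the opening of protocol section 11, the SAP prevails.

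SAP 10.2 lets a measured FEV1 be set to missing only "if they were the result of poor quality spirometry efforts". It also removes patients with a major deviation on the Test or Reference day, and drops placebo-day data after a major deviation on that day. The grading is elsewhere: "Each deviation will be further classified as major/minor as defined in the protocol deviation guidelines" (SAP 13.2).

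The two sensitivity analyses in SAP 9.11 are ones "where the missing data rules for the tail end of the profile will be based on the following": AUC to the last non-missing point, or baseline substituted for the missing values.

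**The concern.** The rule needs missing data, and a site that follows protocol 8.1.1 will not produce any. Two readings remain, and neither meets the SAP's stated aim.

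**Reading A, literal.** Measured post-rescue values stay in the AUC. This holds in the ITT superiority analysis, which has no deviation filter (SAP 10.1). It holds in the per-protocol (PP) bioequivalence analysis whenever rescue is not graded a major deviation.

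**Reading B, by intent.** Post-rescue values are treated as missing. The 9-of-11 condition then blocks the rule for most rescue times, and the SAP does not state the outcome below 9.

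In the ITT tests, boosted placebo profiles shrink both differences from placebo. That costs precision and some power but cannot create a false superiority claim. In the bioequivalence (BE) analysis, the issue matters chiefly if rescue rates differ between Test and Reference: an excess on Test is partly hidden, and an excess on Reference costs the sponsor power. Both sensitivity analyses act only on missing values, so neither would show the effect of measured post-rescue readings.

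**Working it through.** **1. Readings left.** SAP 9.7 schedules 11 postdose readings: 5 and 30 min, then 1, 2, 4, 6, 8, 10, 12, 23 and 24 h. This matches the 11 in the SAP's condition.

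| Rescue between | Left if all later readings are set aside | Left if only 6 h after rescue is set aside |
|---|---|---|
| 6 and 8 h | 6 | 8 |
| 8 and 10 h | 7 | 9 |
| 10 and 12 h | 8 | 10 |
| 12 and 23 h | 9 | 9 or more |

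Earlier rescue leaves 5 or fewer in the first column and 8 or fewer in the second. With all later readings set aside, the condition fails for any rescue before the 12 h reading. With only the protocol's 6-hour SABA withholding interval set aside, it still fails for any rescue before the 8 h reading.

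**2. Weight of the affected readings** (trapezoidal rule, SAP 9.2).
- 12 h: (12 − 10)/2 + (23 − 12)/2 = 6.5 h; 6.5/24 = 27.1%.
- 23 h: 6.0 h (25.0%). 24 h: 0.5 h (2.1%).
- Together: 13.0/24 = 54.2%.

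**3. Reading A, one profile.** Assume rescue raises readings within 6 h by 0.05 to 0.20 L (not in the documents).
- Rescue at 9 h affects 10 h (weight 2.0 h) and 12 h: 8.5 × 0.05 to 0.20 = 0.43 to 1.70 L·h.
- Rescue at 11 h affects 12 h only: 6.5 × 0.05 to 0.20 = 0.33 to 1.30 L·h.

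**4. The plan's own power figure.** Inputs from SAP 11.5: 238 PP patients, intra-patient CV 0.3642, between-patient CV 1.21, expected ratio 0.90. In units of the reference mean,

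SE(Y_T − 0.8·Y_R) = √[(0.3642² × 1.64 + 1.21² × 0.04)/238] = 0.0341.

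Power = Φ(0.10/0.0341 − 1.645) = 0.90, as the SAP states. At CV 0.60 the SE is 0.0522.

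**5. Reading B with rescued periods lost.** Let p_T and p_R be the rescue rates and f the AUC of a rescued period as a share of its usual value. All three are assumptions. At a true ratio of 0.80,

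observed ratio = 0.80 × [(1 − p_R) + p_R·f] / [(1 − p_T) + p_T·f]

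false acceptance = Φ((observed ratio − 0.80)/SE − 1.645).

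| p_T vs p_R | f = 0 | f = 0.52 | f = 0.75 |
|---|---|---|---|
| 5% vs 0%: observed ratio | 0.842 | 0.820 | 0.810 |
| false acceptance, CV 0.3642 | 34% | 14% | 9% |
| false acceptance, CV 0.60 | 20% | 10% | 7% |
| 5% vs 3%: observed ratio | 0.817 | 0.808 | 0.804 |
| false acceptance, CV 0.3642 | 12.5% | 8% | 6% |
| Equal rates | 5% | 5% | 5% |

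Opposite split (Reference 5%, Test 0%, f = 0.52, true ratio 0.90): 0.90 × 0.976 = 0.878; Φ(0.078/0.0341 − 1.645) = 0.74, so power falls from 90% to 74%.

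**6. Superiority.** SE of Test minus placebo = 0.3642 × √(2/238) = 0.033 of the reference mean. The difference detectable with 90% power is 0.033 × 3.24 = 0.11. At CV 0.60 these are 0.055 and 0.18.

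**The case against.** - **The error rates rest on stacked assumptions.** They need Reading B, lost periods, rescue not graded major, unequal rescue rates and a low AUC in rescued periods. With 3% vs 2% the same formula gives about 8%, 6% and 5.6%. No BE effect is calculated for Reading A, the literal one. This stands: the figures are illustrations.
- **The 9-of-11 sentence may cover only gaps inside the profile.** It opens the interpolation paragraph, and the tail rules follow under their own lead-in. This is possible, but the wording is general and stands ahead of all the rules. On the narrow reading, measured post-rescue values still enter the AUC.
- **Deviation handling may deal with rescue.** If the guidelines grade it major, PP exclusion removes it from the BE analysis. That source is not in these documents, and exclusion does not reach the ITT analysis.
- **A period below 9 is implicitly non-evaluable.** SAP 10.1 requires sufficient data and SAP 11.5 counts evaluable AUCs. That is implied, not stated.
- **Protocol 9.2.1.1 need not conflict with 8.1.1.** Its "If these criteria have not been met, the patient should have the visit rescheduled" can be read as a readiness check before testing starts. This is fair; the point is minor, but the two passages should be reconciled.
- **Overwriting the whole tail discards late readings that may be free of SABA effect.** This is true, and the resulting added variance and loss of BE power have not been calculated.

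**Conclusion.** The concern holds. As written, the rescue rule has nothing to act on when sites follow the protocol, so the primary AUC credits improvement after rescue that SAP 9.11 means to exclude. This rests on the text alone and needs no assumed rate. The block by the 9-of-11 condition holds on the natural reading of that sentence.

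The size of the bias is unknown because the documents give neither a rescue rate nor a SABA effect. Superiority over placebo is unlikely to change. For BE, equal rescue rates leave the error at 5% in the lost-period calculation; unequal rates move it as tabulated, provided rescue is not removed as a major deviation. This should be fixed, because otherwise programmers could derive the primary endpoint in different ways, and settling it after unblinding would be a data-dependent choice.

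**What to change.** Amend SAP 9.11 before unblinding:
1. Set FEV1 recorded after rescue on that test day to missing before the AUC is calculated, then apply the existing minimum-value rule.
2. Do not count these values as missing for the 9-of-11 condition.
3. State how a profile below 9 of 11 for other reasons is handled.
4. State whether rescue on a Test or Reference day is a major deviation.

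Add two sensitivity analyses: one with all values as measured, and one setting aside only readings within 6 hours of rescue, filled by the existing 9.11 rules with the same exemption. Report rescued periods by treatment. Reconcile protocol 8.1.1 and 9.2.1.1 with SAP 9.11 and 10.2. No change to patient care is proposed.

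The cost is a short edit, a flag from recorded rescue times and two more model runs. The downside is that rescued periods get lower AUCs. A rescue just after the 5-minute reading replaces 10 of 11 values. After a rescue at 9 h, the overwritten 23 and 24 h readings carry 6.5/24 = 27% of the weight. The 6-hour analysis shows how much that matters.

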10.0 Analysis Population

10.1 Intention-to-Treat

The ITT analysis population will adhere as closely as practically possible to the intention-to-treat (ITT) ideal, and will be based on data from all patients who were randomized, took at least one dose of study medication and contributed sufficient data for at least one efficacy endpoint to be calculated. The ITT analysis population will be the primary analysis population used for the demonstration of the superiority of the active treatments to placebo. In this population, treatment will be assigned based upon the treatment to which patients were randomized regardless of which treatment they actually received.

10.2 Per Protocol

The Per Protocol (PP) analysis population will be the primary analysis population used for the determination of BE between the Test and Reference products. The PP analysis population will exclude patients from the ITT population who have major protocol deviations in Part 1 of the study on either the Test treatment day or the Reference treatment day. Patients may have a major protocol deviation on the Placebo treatment day and still be

Sponsor: Lupin Inc.
Protocol no: TB-DPI-301

included in the Per Protocol population that will be used to assess BE although data from the Placebo day will be excluded from the analysis.

All patients with a major protocol deviation will be identified before the study blind is broken, and the removal of a patient from a treatment period will be documented within the clinical trial management system's protocol deviation file. In addition, individual FEV1 values from a patient may be removed from their 24-hour serial curve, including the 2 predose measurements, if they were the result of poor quality spirometry efforts. In those cases, the value will be set to missing and missing value rules applied as described in [Section 9.11](#).

10.3 Safety

The safety analysis population will include all patients who receive at least one dose of any one of the randomized investigational products and for whom data have been collected after randomization.

10.4 Part 2 of the Study

All patients who begin treatment during the open-label portion of the study.

10.5 All Subjects

All patients who sign consent form for the study.

10.6 All Randomized Subjects

All patients who are randomized in the study.

11.0 Interim Analysis

11.1 Objective of the Interim Analysis

A blinded interim look at the data will be made in order to check the assumption about intra-patient variability made when estimating sample size with the possibility of increasing sample size, if necessary, to maintain 90% power. The interim look is planned when 150 of the planned 240 randomized patients have completed Part 1 of the study. Issues impacting the choice of a final sample size will include the estimate of intra-patient variability and the estimate of the ratio of the means demonstrated in the pivotal PK study. The interim analysis will be conducted by PRA Health Sciences.

11.2 Endpoint for the Interim Analysis

The endpoint for the interim analysis is the baseline-adjusted FEV1 AUC_{0-24h} on the single-dose treatment days.

11.3 Interim Analysis Population

The PP population will be used for the interim analysis. Patients who have major protocol deviations will be excluded from the interim analysis population.

Sponsor: Lupin Inc.
Protocol no: TB-DPI-301

11.4 Sample Size Re-calculation for the Interim Analysis

The original sample size estimate is based on an assumed intra-patient variability to which sample size estimates are very sensitive. From a review of studies on clinicaltrials.gov, there were a number of estimates available of between-patient variability for baseline-adjusted FEV1 AUC₀₋₂₄. From the 12 studies reviewed, the mean CV for the variable was 121%. Within-patient variability is generally much less than between-patient variability. As a starting point for the sample size estimation it was assumed that the within-patient variability would be about 50% of the between-patient variability, or a CV of 60%. A blinded interim review of the data is planned to assess if this reduction is obtained. The missing data methods outlined in [section 9.11](#) will be applied for the interim analysis, with the following exceptions: (1) no imputation would be performed during peak times, and (2) missing data at the tail-end of the spirometry profile would use Last Observation Carried Forward (LOCF) methods.

11.4.1 Intra-patient CV Estimation

In order to perform the interim sample size re-estimation (by nQuery7), the between-subject CV and the intra-subject CV need to be estimated using the interim data:

- Between-subject CV (CV_B) = σ_B / μ_R
- Intra-subject CV (CV_I) = σ_I / μ_R

Where σ_B is between-subject variance, σ_I is intra-subject variance and μ_R is the Least Square Mean (LSMean) of the reference (SPIRIVA) treatment.

To get estimates for σ_B , σ_I and μ_R , a mixed model can be used with a fixed effect for period and a random effect for patient using the PP population. The typical crossover model fixed effects for treatment and sequence are not included because the treatment codes are to remain blinded.

The SAS procedure to be used is:

```
proc mixed data=interim;
  class usubjid period;
  model Baseline-adjusted FEV1 AUC0-24h = period/ solution;
  random usubjid;
run;
```

where

- usubjid = patient
- period = treatment period

Sponsor: Lupin Inc.
Protocol no: TB-DPI-301

In the SAS output, the covariance (COV) estimate of σ_B will be called “Usubj_{id}” and σ_1 will be called “Residual”. Normally we estimate μ_R as the LSMeans for the reference (SPIRIVA) treatment, however, since this is a blinded estimation, we could instead use the estimate of CV_B from the Protocol as: $\mu_R = \sigma_B / 1.21$. Then, we use that estimate of μ_R to estimate $CV_1 = \sigma_1 / \mu_R$.

One downside of this approach is that it includes placebo which will almost surely inflate the intra-subject variance (and hence CV_1). The effect could be dramatic if the two active treatments are efficacious (i.e., much different from placebo). It should not affect between-subject variance.

To address this concern, 2 methods will be used to estimate the intra-subject variability and CV:

- Use the subject’s AUC values from all 3 treatments to estimate the intra-subject CV. This method will provide a liberal (i.e., likely too large) sample size estimate since the placebo data will increase the intra-subject CV.
- Only use the data from the two “closest” AUC values from each subject’s data to estimate the intra-subject CV. This approach mimics the inclusion of only the two active treatments in the sample size re-estimation (i.e., akin to excluding placebo). This method will produce a conservative (ie, likely too small) sample size estimate.

A decision on the sample size re-estimation will be made based on the results from the above 2 methods.

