11.4.2 Sample Size Re-calculation

Once intra-patient CV is identified, sample size re-calculation will be performed using nQuery 7.0 with the following parameters:

- Power = 90%
- Expected ratio = 0.88 to 1.12
- Lower equivalence limit = 0.8
- Upper equivalence limit = 1.25
- Test significance level alpha (one-sided) = 0.05
- CV between subjects = 1.21 (assumption from the protocol)
- CV within subjects = new number calculated from the above mentioned model based on the actual interim data

The results of the 2 new sample size estimates (one based on data from all treatments and the other based on the 2 “closest” data values) will be available after using the above parameters. The estimate of the ratio of the means demonstrated in the pivotal PK study will help inform which expected ratio will be used in the final sample size chosen.

Sponsor: Lupin Inc.
Protocol no: TB-DPI-301

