11.5 Results of the Interim Analysis

The final interim analysis report was dated 01Sep2017, and is attached in [Appendix 3](#).

A total of 122 (of the 150) patients had 3 treatment periods with evaluable AUC data, and these data were included in the “closest” AUC analysis. Based on the results, the intra-patient CV was 0.3642 and the between-patient CV was 1.210. The table below summarizes the crossover design of two one-sided tests (TOST) for difference or ratio of means:

	Protocol	Closest AUC (N=122)		
		Low ratio	Ratio=1	High ratio
Test significance levels, α (one-sided)	0.050	0.050	0.050	0.050
Lower equivalence limit for μ_T / μ_R, D_L	0.800	0.800	0.800	0.800
Upper equivalence limit for μ_T / μ_R, D_U	1.250	1.250	1.250	1.250
Expected ratio, μ_T / μ_R	1.000	0.880	1.000	1.120
Coefficient of variation between subjects, CV_B	1.210	1.210	1.210	1.210
Coefficient of variation, intrasubject, CV_i	0.600	0.3642	0.3642	0.3642
Power (%)	90	90	90	90
n total	178	372	78	220

Results obtained from nQuery Advisor® 7.0

Based on the results, sample size estimates range from:

- a total of 372 across the six treatment sequences if the expected ratio of test to reference is 0.88
- a total of 220 patients across the six treatment sequences if the expected ratio of test to reference is 1.12

Assuming an expected ratio of means of 0.90 based on results from the pivotal PK study, an estimated 238 per-protocol patients would be needed to demonstrate equivalence between the test and reference products. Therefore, the Sponsor plans to randomize a total of approximately 378 patients (instead of 240 patients specified in the protocol with Amendment 1, dated 11May2017), to allow for a potential 30% withdrawal rate or loss from the per-protocol population due to protocol deviations.

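### The interim CV rule in SAP 11.4.1 is worded with variances, and SAP 11.5 reports the assumed between-patient CV of 1.210 as a result, so the 90% power at 238 patients is conditional

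*SAP*

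**What the plan says.** SAP 11.4.1 sets CV_B = sigma_B/mu_R and CV_I = sigma_I/mu_R. It says that sigma_B "is between-subject variance", describes sigma_I in the same way, and reads both from the patient and residual covariance estimates of PROC MIXED. It mentions no square root. Because the treatment codes stay blinded, the reference mean is not estimated: "since this is a blinded estimation, we could instead use the estimate of CV_B from the Protocol as" mu_R = sigma_B/1.21. CV_I then follows from that mu_R.

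The same section gives two ways to obtain the within-patient component. One uses all three AUC values per patient. The other uses only the two closest, and of it the SAP says: "This method will produce a conservative (ie, likely too small) sample size estimate". It adds: "A decision on the sample size re-estimation will be made based on the results from the above 2 methods".

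SAP 11.4.2 lists "CV between subjects = 1.21 (assumption from the protocol") among the inputs. SAP 11.5 then states: "Based on the results, the intra-patient CV was 0.3642 and the between-patient CV was 1.210". Its table shows the closest-pair analysis (N=122) beside the protocol column. With an expected T/R ratio of 0.90 taken from the pivotal PK study, it concludes that "an estimated 238 per-protocol patients would be needed to demonstrate equivalence between the test and reference products", and plans about 378 randomized in place of 240.

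**The concern.** There are three linked problems.

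1. **The formula as worded does not give a CV.** A CV is a standard deviation over a mean. Using variance components in both places gives CV_I = 1.21 × sigma_I²/sigma_B². Units cancel in that ratio, so a units check would not catch the slip. The supplied text shows no sigma values, so a reader cannot tell on which scale 0.3642 was computed.

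2. **An assumption is reported as a finding.** Setting mu_R = sigma_B/1.21 makes CV_B equal to 1.21 for any data. SAP 11.4.2 says so correctly. The sentence in 11.5 does not.

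3. **The power statement omits its conditions.** The interim look was meant to check an "assumed intra-patient variability to which sample size estimates are very sensitive". What it yields is the ratio sigma_I/sigma_B, and CV_I inherits the untested 1.21 as a multiplier. The ratio also comes from the method that the SAP expects to understate the sample size. SAP 11.5 names that method but repeats neither caveat beside the 238.

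**Working it through.** **Inputs (SAP 11.4.2 and 11.5).** One-sided alpha 0.05; limits 0.80 and 1.25; power 90%; CV_B 1.21; CV_I 0.3642; T/R 0.90; 378 randomized; 30% loss.

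**Method.** Two one-sided tests on the ratio of means in a crossover. For theta = 0.80 and 1.25, with the reference mean scaled to 1,

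Var(Y_T − theta·Y_R) = [CV_I²(1 + theta²) + CV_B²(1 − theta)²]/N,

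with noncentral t on N − 2 df and the smallest even N that reaches 90%. Both CVs must be on the SD scale.

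**Reproducing the plan.**

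| T/R | CV_I | N computed | N in SAP |
|---|---|---|---|
| 1.00 | 0.60 | 178 | 178 |
| 0.88 | 0.3642 | 372 | 372 |
| 1.00 | 0.3642 | 78 | 78 |
| 1.12 | 0.3642 | 220 | 220 |
| 0.90 | 0.3642 | 238 | 238 |

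Power at 238 is 90.02%. After 30% loss, 378 × 0.70 = 264.6, so 264 per-protocol patients remain, with 92.5% power at the SAP's inputs.

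**Variance wording.** At the protocol's values (CV_B 1.21, CV_I 0.60), the rule read literally returns 1.21 × 0.60²/1.21² = 0.2975, not 0.60. Conversely, if 0.3642 had been computed from variances, the SD-scale CV_I would be 1.21 × √0.301 = 0.664. That would need N = 672, with 54% power at 238. If SDs were used, 238 stands, given CV_B = 1.21.

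**Dependence on 1.21.** The interim fixes only 0.3642/1.21 = 0.301, so CV_I = 0.301 × CV_B. At T/R 0.90:

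| True reference mean relative to sigma_B/1.21 | CV_B | N for 90% | Power at 238 | Power at 264 |
|---|---|---|---|---|
| 25% above | 0.968 | 154 | 98% | 99% |
| as assumed | 1.21 | 238 | 90% | 92.5% |
| 10% below | 1.344 | 294 | 84% | 87% |
| 25% below | 1.613 | 422 | 71% | 75% |

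N grows roughly with the square of CV_B: 294/238 = 1.235 against (1.344/1.21)² = 1.234.

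**Dependence on the closest-pair CV_I.** With CV_B held at 1.21 and T/R 0.90:

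| CV_I | N for 90% | Power at 238 | Power at 264 |
|---|---|---|---|
| 0.3642 | 238 | 90% | 92.5% |
| 0.40 | 278 | 86% | 89% |
| 0.45 | 336 | 79% | 83% |
| 0.50 | 404 | 73% | 77% |
| 0.60 | 558 | 60% | 64% |

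**Direction of the closest-pair bias.** I simulated 400,000 patients with normal data, between-patient SD 1, within-patient SD 0.496 (the protocol's 0.60/1.21), and one of the three values shifted down by 0, 0.4 or 0.8. The apparent within/between SD ratio was 0.19, 0.21 and 0.26 against a true 0.496. This supports the SAP's own statement about direction. It does not estimate the bias in this trial.

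**The case against.** The strongest reply is that this is wording. The symbols are the usual ones for standard deviations, and nothing shows that variances were used. Extending the simulation above, a variance reading needs an apparent closest-pair SD ratio of √0.301 = 0.549, while a true within/between ratio of 1.5 produced only 0.43 at the largest shift, 0.8. That argues, within the model, against variances having been used, because the SAP expects within-patient variability to be much the smaller.

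Further, 11.4.1 and 11.4.2 disclose the source of 1.21, and the 11.5 table repeats it in every column. The closest-pair caveat appears in 11.4.1 and the method is named in 11.5. Every sample size depends on its assumed variability. The planned 378 leaves a margin: 264 per-protocol patients keep 90% power up to a CV_B of about 1.28 (ratio fixed) or a CV_I of about 0.39 (CV_B fixed). The interim report in Appendix 3, which is not in the supplied text, may contain the sigmas and the all-treatment result.

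Much of this stands. The disclosures are real, the margin is real, Appendix 3 may answer the scale question, and the ranges above are assumed because the documents give no spread for the 12 source studies. It does not remove the point. The rule as written is wrong. The 11.5 sentence contradicts the 11.4.2 label. The margin ends at modest departures from two inputs, one untested and the other expected by the SAP to be too low.

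**Conclusion.** The concern holds and should be fixed. The SAP's arithmetic is right: 238 follows from its inputs. What is wrong is the formula's wording in 11.4.1, the presentation of 1.210 as a result in 11.5, and a 90% power figure given without its two conditions.

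Over the ranges shown, power at 238 runs from 98% (CV_B 0.968) to 71% (CV_B 1.613) with the within/between ratio fixed, and from 90% (CV_I 0.3642) to 60% (CV_I 0.60) with CV_B fixed. These are illustrations at T/R 0.90, not tolerances. The CV_B effect can go either way. The closest-pair effect, by the SAP's own account, goes towards too few patients. Only the stated power is affected. Type I error and the final bioequivalence analysis are untouched.

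**What to change.** In SAP 11.4.1, define sigma_B and sigma_I as the square roots of the PROC MIXED variance components.

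In SAP 11.5:

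- confirm that 0.3642 was computed on the SD scale, and recompute it if not;
- label 1.210 as assumed from the protocol;
- state that 90% power at 238 depends on CV_B = 1.21 and on the closest-pair CV_I;
- tabulate N and power at T/R 0.90 over a stated range of both CVs, including the all-treatment CV_I that 11.4.1 calls for, or cross-refer to Appendix 3 if it is there.

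The cost is SAP wording and a recalculation from existing blinded interim output. It needs no unblinding and no new data, and no change to enrolment is asked for.
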